3/27/2019	12/17/2019	2.0	
 
Start enrollment for 400 participants in Milwaukee
 
Changes based on pilot study findings
 
Change online consent to face-to-face
 
Remove Pap test in last 12 months as an exclusion criterion
 
Changes to specimen delivery
 
Co-I contact info updated
 
Add transmen to Inclusion Criteria
 
Changes to swabbing protocol and processing
 
Changes to CASI questions
 
Edits for clarity
 
Stratification removed from stratification scheme
 
	[name]
1/3/2020	5/20/2020	2.0	Add Spanish language     material (no protocol     change needed)	[name]
5/20/2020	8/25/2020	3.0	
 
COVID-19-Induced         Consent Change
 
Remote consenting         instituted due to COVID-         19.
 
Consent ICF changed to         reflect changes in the         consenting process and         related changes to the         Baseline and Post Swab         CASIs.
 
	[name]

			T T
			
 
4. Screening limit increased to 1200 and consenting limit raised to 500 to accommodate no shows between remote consenting and Visit 1.
 
5. COVID-19 questions added to surveys in addition to minor wording changes to some survey questions.
 
6. Co-investigator [name] worksite updated.
 
7. Insurance requirement removed.
 
8. Use of voicemail added.
 
9. AIDS Resource Center of Wisconsin's new name Vivent Health added.
 
10. Biometric measurements moved to clinic location
 

8/26/2020	1/12/2021	4.0	1. Updated recruitment section to include referral program 2. New recruitment materials 3. Remove FDA language 4. Update Spanish ICF
6/17/2021	7/27/2022	4.0	1. Recruitment material, training medical students, ICF-protocol consistency, added survey questions, and Spanish translation
01/03/22	1/3/2022	4.1	
 
Add analysis of deidentified data.
 
Add language for blood draws at HRA as previously approved by MCW IRB
 
Allow up to 4 calls to ppts at the 12 month time point to encourage participation.
 

01/05/2022	1/10/2022	4.2	1. New Recruitment material	[name]
1/30/2022	2/7/2022	4.3	Press Release used to support recruitment.	[name]
2/23/2022	5/18/2022	4.4	Letter to ppts about ANCHOR results	[name]
Various	5/25/2022 7/15/2022 11/14/2022	n/a	Three amendments to increase numbers of total screened and consented.	[name]
06/20/2023	7/10/2023	4.5	1. Add MUSC as getting a deidentified dataset 2. New survey to participants to ask about interest in follow-up study	[name]

#### STUDY SYNOPSIS

A randomized, non-blinded study of compliance with annual home-based vs clinic-based DNA screening to detect anal canal precancers among 400 Milwaukee HIV+ and HIV- men who have sex with men (MSM) and transgender persons.

This is a prospective, randomized, two-arm clinical study to evaluate compliance with annual home-based vs clinic-based DNA screening of anal canal exfoliated cells among Milwaukee HIV+ and HIV- MSM and transpersons aged ≥25 years. At study entry, persons randomized to arm 1 will receive a home-based collection kit in the mail at 0 and 12 months and those in arm 2 will attend a clinic where a clinician will collect the exfoliated cell specimen at 0 and 12 months. Then, persons will receive HRA-directed biopsy to assess precancerous lesions by study arm. We hypothesize that a majority of persons will comply with annual screening with increased compliance among persons in the home-based arm vs clinic-based arm.

We will test our hypothesis with 3 specific aims:

- 1) Determine persons' compliance with annual anal HPV DNA specimen collection. The primary endpoint is compliance with swabbing at both baseline and 12 months.
- 2) Determine factors associated with annual screening compliance.
- 3) Establish the proportion of persons in each arm who agree to have HRA.

The current research will deliver:

- The first estimates of compliance with an annual biomarker screening program among MSM and transpersons;
- The first estimates of the relative ability of home-based screening to increase annual compliance;
- Evidence of the influence that home-based vs clinic-based screening has on the uptake of HRA-directed biopsy.

The proposed research could indicate that annual HPV DNA screening and subsequent HRA are acceptable to MSM and transpersons; thus, we will determine how high-risk persons are identified for HRA in light of limited HRA resources. The duration of each participant's activities is expected to be 12 months. The study is expected have participant activity from 2019 to 2023.

## **OBJECTIVES:**

**Primary Objective:** To determine compliance with annual DNA-based screening among Milwaukee HIV+ and HIV- MSM and transpersons, aged  $\geq 25$  years.

# **Secondary Objectives:**

- To determine estimates of the relative ability of home-based screening to increase annual compliance.
- To estimate the influence that home-based vs clinic-based screening has on the uptake of HRA-directed biopsy.
- To estimate the association between high-risk HPV persistence and anal high-grade squamous epithelial lesions.
- To estimate the association between host and viral genome methylation and anal highgrade squamous epithelial lesions.

# LIST OF ABBREVIATIONS

CAB	Community Advisory Board
CAIR	Center for AIDS Intervention Research
CASI	Computer-Assisted Self-Interview
CTEP	Cancer Therapy Evaluation Program
DARE	Digital Anal Rectal Exam
HBM	Health Belief Model
HPV	Human papillomavirus
HRA	High-Resolution Anoscopy
MSM	Men having sex with men

#### **BACKGROUND**

MSM are at much greater risk of anal cancer which is the most commonly diagnosed HPV-associated anogenital cancer other than cervical cancer. While total anal cancer incidence among men and women is rare (~1.8/100,000), the rate has almost tripled in the last three decades and is dramatically higher among both HIV- and HIV+ MSM (e.g., 131/100,000 for HIV+). Also, African-American males with HIV have a disproportionate risk for anal cancer and worse survival than non-Hispanic white males with HIV. However, if anal cancer is detected at an early stage, the 5-year survival rate sharply increases while delayed diagnosis can result in sphincter dysfunction and permanent colostomy. As with cervical cancer, if anal cancer precursor lesions are successfully removed, then morbidity and mortality will likely decline.

Persistent anal HPV infection is the primary cause of anal cancer which is a common cancer among MSM. Anal cancer screening (either Digital Anal Rectal Exam (DARE) or Pap cytology followed by high-resolution anoscopy) is standard of care for HIV+ MSM and recommended by expert opinion for HIV- MSM and is increasingly offered by clinics. But most HIV+ and HIV- MSM do not screen. Since home-based self-sampling increases rates of cervical cancer screening and self-sampling is acceptable to MSM, it is important to investigate home-based screening for anal cancer among MSM.

In addition, data on anal cancer incidence among transpersons is sparse due to lack of data collection on gender identity; however, there are data indicating that HPV prevalence among MSM and transwomen is comparable. In addition, there are data indicating a similarly high (or higher) HIV prevalence among transwomen compared to MSM. Finally, there are no data to our knowledge on anal HPV among transmen, including transmen who have sex with men.

No one has assessed compliance with annual home-based anal canal self-sampling which is required to detect 12-month persistent HPV infections. Cervical cancer screening protocols increasingly rely on a molecular biomarker (e.g., HPV DNA testing). DNA collection works well with home-based kits, but one-time DNA screening is of no value for MSM and transwomen given their high HPV prevalence; however, an experiment of *repeated* DNA screening can detect persistent HPV infection. High-risk HPV DNA persistence helps predict appearance and lack of spontaneous clearance of precancerous lesions.  Identifying persons at highest risk for precancerous lesions is particularly needed since there is very poor infrastructure for HRA in the US and elsewhere. 

There has been no testing of annual home-based screening for high-risk HPV DNA at the anal canal. Annual self-screening for high-risk DNA tests enables the detection of high-risk HPV persistence which should increase the lower specificity of a single DNA screening for precancerous lesions. Screening at 0 months and 12 months is not an example of sequential screening since there is only one outcome of the two tests: a positive or negative result for persistent high-risk HPV.

We will take advantage of the ability to test another biomarker by also testing for host DNA and HPV DNA methylation using the same specimens that will be tested for HPV DNA. Once the specimen is returned to MCW, it will be aliquoted into five cryovials. The first will be used for

HPV DNA genotyping, the second will be used for host DNA and HPV DNA methylation testing while the third will be archived. DNA methylation testing of HPV and human genes accurately predicts cervical HSIL. Methylation patterns of HPV-16 and the host tumor suppressor gene EPB41L3 will be studied to determine if higher levels of methylation are associated with HSIL.

Within cervical cancer screening, the transition to DNA tests from Pap tests also provides increased opportunity for self-screening since DNA specimens are more feasible to collect than Pap specimens given their greater sensitivity. Home-based self-swab programs may also be cost-effective and also increase access for those less likely to visit clinics due to men's greater tendency than women to avoid doctors and avoid ano-genital exams due to embarrassment. Unease may be more acute among African Americans who may have heightened embarrassment.

Our prospective design and use of a highly sensitive assay also present us the opportunity to detect deficiencies in specimen collection from either participant or clinician (as measured by the presence of  $\beta$ -globin). Specimen adequacy for self-collected and clinician-collected cytology are comparable,  $\geq 80\%$ ,  $^{30,\,31}$  and given increased sensitivity of HPV DNA collection,  $^{21}$  we expect DNA specimens would yield better adequacy.  $^{32,\,33}$  To enhance quality control, we will compare the adequacy of sample collection between providers and sites after 40 samples have been collected. Our ability to compare specimen adequacy of home-based self-collected vs clinician-collected annual specimens is itself a strong contribution to the literature; however, we emphasize that Aim 1 and 2, compliance with a screening protocol and factors associated with compliance, are in no way dependent on the adequacy of the specimen. The compliance findings will inform the development of repeated anal cancer screening protocols deemed efficient and accurate; thus, no matter the biomarker, health care providers and researchers will find the current study results important as benchmarks for annual anal cancer screening.

To our knowledge there has been no assessment of a mailed, culturally-competent home-based anal canal self-collection kit for persons at increased risk for anal cancer. Under the direction of PI [name], our prior anal cancer-screening R21 (PI, [name]; NCI 1R21CA181901-01A1) recruited 200 MSM. While only 26% of these men reported prior anal cancer screening, 93% of men said they would use a swab to collect a home-based anal sample, and of those, 98% said they would do it at least annually. Thus, there is compelling evidence for MSM doing home-based repeated screening but there are no empirical data.

We chose annual screening 1) based on our studies estimating that 12% of MSM will have 12-month persistence with high-risk HPV (suggesting an increased risk for anal cancer and thus needed HRA), 2) given expert opinion on anal screening intervals for HIV+ MSM, and 3) because it is a familiar interval that may encourage repeat screening.

While our primary objective is to determine compliance with annual anal cancer screening, we want to understand 1) non-modifiable factors to better understand which vulnerable populations to target for future interventions and 2) modifiable factors (beliefs, attitudes, and knowledge) so that future studies might develop interventions addressing those determinants. We are using the Health Belief Model (HBM), as a framework to understand the determinants of screening. If there are other determinants pointing to constructs not in the HBM, our CASI will allow us to identify those constructs and then address those determinants in future investigations. Given the

personal nature of some questions on the surveys, we are using a CASI platform to increase the likelihood of candid and accurate responses. CASIs are considered highly reliable survey methods for collecting sensitive data within multi-lingual and multi-cultural cohorts. 47-50

In our prior R21, over 95% of 173 men reported that they could do annual anal swabbing to screen for anal cancer (unpublished data). Also, HIV+ and HIV- men showed no difference in their *intentions* to adopt annual swabbing (95% and 97%, respectively, p=0.51) as did men regardless of age, race, ethnicity, marital status, or concern about anal cancer. However, we believe HIV status will influence *actual* compliance since most (77%) believed HIV increases the risk for anal cancer; thus, we propose now to directly measure screening *behavior* to elucidate our findings of *intentions* to screen. As another example, co-Investigator [name], et al. found an increased return of anal samples from women reporting receptive anal sex. Our R21 data among MSM shows no such difference in intentions to do self-sampling based on receptive anal sex. We now intend to test that association among MSM and transpersons. Knowing the factors that increase compliance within a behavioral framework will help create interventions that increase screening uptake among persons at increased risk for anal cancer.

[figure not shown]
In addition to a biomarker, a procedure like HRA with directed biopsy is needed to identify precancerous lesions or cancer in the anal canal; however, some persons may refuse to undergo the invasive procedure of HRA with biopsy. The studies are equivocal with regard to HRA acceptability among MSM with one finding significant pain and bleeding with HRA, and a second finding little. The current study will assess a real-world scenario where a certain proportion of persons, even though potentially compliant with annual screening, may decide to forgo HRA.

We are keenly aware that introduction of the more invasive HRA may also influence those who choose to consent and those who are compliant with repeated sampling; thus, we will collect reasons for declining consent and data on those lost to follow up.

Our proposed experimental design in Aim 1 and 2, plus our prior work in HPV natural history and anal cancer screening positions us to identify 12-month persistence among persons and make important observations about which of these HPV-persistent persons complied with HRA.  With this design we can efficiently test important questions: Will MSM and transpersons comply with annual biomarker screening? Will home-based sampling increase compliance? What other factors are associated with repeated annual screening? What proportion of persons will agree to clinic-based HRA-directed biopsy (the definitive test for precancerous lesions) after home-based self-sampling? What HPV DNA biomarkers efficiently detect anal high-grade lesions? Answers to these questions support our long-term goal of reducing morbidity and mortality from anal cancer given an increasing incidence of disease and very limited impact of HPV vaccination on adults given very low uptake to date.

#### STUDY SCHEMA

Figure 1. The PAC Self-Swab Study visits overview

#### PARTICIPANT RECRUITMENT AND ENROLLMENT

Participants must meet all stated eligibility criteria.

#### Inclusion Criteria

- Be  $\geq$  25 years of age
- Sex at birth is male or gender identity is a transgender person
- Acknowledge sex with men in the last 5 years, or identify as gay or bisexual
- Understand and be willing to give informed consent
- Be willing to be randomized and able to comply with the protocol
- Spanish and/or English speakers/readers, and
- HIV+ or HIV-

# **Exclusion Criteria**

- Not acknowledge sex with men in the past five years and not identify as gay or bisexual
- Use of anticoagulants other than Aspirin or NSAIDS
- Prior diagnosis of anal cancer
- Plans to move within 12 months
- Not Milwaukee metro residents
- Not willing to attend one of the designated study clinics at baseline, or
- Inability to give informed consent.

Persons who have had HPV vaccination will not be excluded.

# Recruitment Procedures

We will recruit participants to engage in a study on anal cancer prevention (with no mention of self-sampling or HRA) in order to attract participants with diverse views about self-sampling and HRA. Study recruiters will use six strategies:

- 1. Social media banner ads, e.g., Grindr, Growlr, Jack'd, and Facebook, to reach MSM and transpersons outside of clinics and thus possibly benefitting more from home-based screening;
- 2. Engagement in clinic waiting rooms serving MSM and transpersons (e.g., Vivent Health) for persons not using social media or websites;
- 3. Distribution of promotional materials in targeted businesses and non-profits; 63, 64
- 4. Word of mouth;
- 5. Presentations to community groups;
- 6. Engagement of participants in a voluntary referral program.

The PAC Referral Program will help direct qualified candidates to the study by incentivizing consented study participants to refer partners, friends and family to be a part of the PAC Study. Specifically:

- 1) Study staff will provide already-consented participants with information about the referral program:
  - a. The referral program is designed to spread the word about PAC Study recruitment to men who have sex with men and transgender persons who have sex with men.

- b. The referral program and the study are entirely voluntary.
- c. If study participants want to help recruit, they can pass along up to five coupons to their partners, friends and family. The study participant may be active in the study or have completed the study.
- 2) Each coupon is stamped with a unique number. Staff members will record which coupon numbers were given to which participants.
- 3) Participants can distribute a digital image or hard copy of the coupons to refer persons to the PAC Study Eligibility Survey in REDCap.
- 4) The referred persons then engage in study activities as anyone else with the exception that they will provide the coupon code to a staff person when attending a consenting session. Study team members will ask 'how did you hear about us?' or 'who can we thank for referring you to the study?"
- 5) The participant who referred the person and provided a coupon to person will receive \$20 for each coupon redeemed up to a maximum of five coupons or a total of \$100. Form of payment, e.g., debit card, gift card or cash app, is up to local site. Sites may decide to pay the referrer after each coupon is received or at regular intervals (e.g., bimonthly).
- 6) The \$20 incentive is received by the referee as long as an eligible referent attends a consenting session. The referent does not have to consent to the study for the referee to receive the incentive.

It is our goal that 38% of participants are African American and 18% are Latino which reflects the racial and ethnic demographics of the City of Milwaukee. It is also our goal that 50% are HIV+. We will record data on:

- Recruitment strategies and process data on item distribution
- Number of website hits and calls
- Number who decline consenting
- Reasons for declining (including HRA)
- Reasons for ineligibility, and
- Those not keeping appointments.

We will collect data from study eligibility before consent occurs, e.g., age and sexual orientation, and then retain those data with no identifying information to describe who was more likely to decline participation. These data will include name, phone number, and email address to allow study staff to invite persons who are eligible to consider enrolling in the study. After consenting is complete, we will collect full contact information. Persons who do not provide contact information necessary for the study, i.e., name, mailing address, email address, and primary phone number will not be officially enrolled.

Given that neither the feasibility of a mailed HPV self-sampling kit nor the optimal form and procedures for such a kit have been established, we will employ a 6-10 member community advisory board (CAB) for guidance. Comprised of both HIV-positive and HIV-negative MSM and transpersons and agency representatives who serve them, we will partner with the CAB to ensure study materials are culturally competent for middle-aged, older, and racial and ethnic minority MSM and transpersons. After training on anal cancer and study objectives, the CAB will provide guidance on recruitment, recruitment materials, internet webpage design, kit design, kit

dissemination, and interpretation of results. It will convene for an inaugural dinner during the first 6 months with regular meetings thereafter.

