#### PARTICIPANT RANDOMIZATION

Persons officially enrolled will be randomized in a 1:1 allocation to either the home- or clinic-based swabbing. Blocked randomization is not necessary due to sample size. The Houston Data Coordinating Center will prepare randomization lists using Stata Version 13 (College Station, TX). The randomization process will occur for a consented participant who has satisfactorily completed the baseline CASI. Given obvious differences of each arm, randomization cannot be blinded to study staff or participants although participant data including study arm will be blinded to lab staff.

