For Aim 3, we will estimate the proportion who agree to HRA (with 95% confidence interval). After genotyping results are available, we will assess the proportion of persons agreeing and not agreeing to HRA who have high-risk persistence. Analysis of HRA CASI data will focus on HRA acceptability and use purposeful modeling strategies as with Aim 2 CASI analyses. Exploratory analysis of de-identified data may also be done by collaborators including the University of Chicago and Medical University of South Carolina.

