# Threats to Validity

For Aim 1 selection bias and loss-to-follow-up are threats to validity; thus, we will recruit without

Table 2. Power to detect odds ratio for varying												
proportion exposed in clinic arm												
Proportion exposed in clinic												
	arm (e.g., HIV+)											
Odds Ratio	0.4	0.5	0.6									
1.50	0.52	0.52	0.49									
1.75	0.79	0.79	0.75									
2.00	0.93	0.92	0.89									
2.25	0.98	0.98	0.96									

reference to home-based screening or HRA to lessen the population of persons with heightened concern and reservations about self-swabbing or HRA. Recruitment will use diverse strategies to select a broad spectrum of MSM and transpersons. Those strategies will be modified if enrolled persons are not racially and ethnically diverse; however, since study participants may still be different than non-participants we will ask participants about enrollment motivation including potential concern about study procedures like HRA.

For Aim 2 our primary CASI instruments will be adapted from validated cervical cancer screening instruments given the absence of validated anal cancer screening instruments. The CASI format will keep information bias and missing data to a minimum. If there are excessive missing data for a covariate, we will use the SAS procedure MI to impute missing values.

For Aim 3, we are keenly aware that selection bias and loss-to-follow-up are threats to validity; thus, questions during eligibility screening and consenting will capture data on reasons for declining study participation and the baseline CASI will provide rich data on those who do not return at 12 months. Specimen validity may suffer if poorly collected or exposed to extreme temperature, but studies find self-swabs generally have high adequacy.

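### Coupon referral can enrol linked participants, but the planned Aim 2 models and the intervals for HRA uptake and overall compliance make no allowance for that linkage

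*Combined protocol and SAP*

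**What the plan says.** Recruitment Procedures: "Study recruiters will use six strategies", of which the paid referral program is one. "Study staff will provide already-consented participants with information about the referral program", and each of them may hand on coupons: "they can pass along up to five coupons to their partners, friends and family". The referrer "will receive \$20 for each coupon redeemed up to a maximum of five coupons or a total of \$100". Referred people then go through the study like anyone else and give their coupon code at the consenting session. Once consented they are eligible to refer in turn, so chains can form. The link is kept: "Staff members will record which coupon numbers were given to which participants".

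Participant Randomization: "Persons officially enrolled will be randomized in a 1:1 allocation to either the home- or clinic-based swabbing".

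Analysis: Aim 1 compares compliance between arms with a Mantel-Haenszel test. Aim 2 fits bivariate and then multivariable logistic regressions, reporting odds ratios with 95% intervals. It adjusts for arm, HIV status, race, age and further confounders. For Aim 3, "we will estimate the proportion who agree to HRA (with 95% confidence interval"). Neither this section nor Sample Size Estimation or Threats to Validity mentions referral groups, a design effect, a robust or mixed-model variance, or any analytic use of the coupon numbers.

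**The concern.** A standard logistic model and a standard binomial interval treat participants as independent. Couples and friends recruited through each other may resemble one another in whether they return swabs, whether they accept HRA, and in HIV status, race and beliefs. Positive correlation of this kind leaves fewer effectively independent observations than the head count suggests.

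What is at stake is the precision of absolute levels and of associations. The Primary Objective is worded as a level of compliance, the Synopsis promises first estimates of it, and Aim 3 is a proportion. In Aim 2, factors enter the multivariable model at p<0.25 and are declared significant at p<0.05. Understated standard errors would therefore produce some false factors, mainly among characteristics shared within a social group.

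**Working it through.** **The plan's own figure.** The plan states no interval, referral share, group size or correlation, so it has no figure on this point to reproduce. Its 84% power (0.72 against 0.54, about 200 per arm) concerns the arm comparison. The pooled normal approximation gives 0.964 at 200 per arm and reaches 0.84 at 125 per arm. That mismatch is a separate matter to reconcile and plays no part below.

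**Inputs.** From the documents: 400 participants, up to five coupons each, individual 1:1 randomization. Assumed: s, the share of the sample in referral groups; m, the group size (m = 6 is one referrer plus five enrolled recruits); ρ, the within-group correlation of the outcome; and a proportion of 0.5.

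**Formulas.** With everyone else a singleton, design effect DE = 1 + s(m − 1)ρ. The interval should be √DE times as wide. Actual coverage of the nominal interval is 2Φ(1.96/√DE) − 1. The half-width under independence is 1.96 × √(0.25/400) = 4.9 points. A simulation (beta-binomial groups, 400 people randomized individually, 8,000 replicates per scenario) checked five of the seven rows.

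| s | m | ρ | DE | √DE | half-width, points | coverage, formula | coverage, simulated |
|---|---|---|---|---|---|---|---|
| 0.10 | 2 | 0.05 | 1.005 | 1.002 | 4.9 | 94.9% | not run |
| 0.25 | 3 | 0.10 | 1.05 | 1.025 | 5.0 | 94.4% | 94.1% |
| 0.50 | 3 | 0.10 | 1.10 | 1.049 | 5.1 | 93.8% | 93.9% |
| 0.25 | 3 | 0.30 | 1.15 | 1.072 | 5.3 | 93.2% | 93.2% |
| 0.50 | 6 | 0.10 | 1.25 | 1.118 | 5.5 | 92.0% | 92.2% |
| 0.50 | 3 | 0.30 | 1.30 | 1.140 | 5.6 | 91.4% | not run |
| 0.50 | 6 | 0.30 | 1.75 | 1.323 | 6.5 | 86.2% | 85.9% |

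**Proportions by arm.** The Synopsis words Aim 3 by arm. Under 1:1 individual randomization about half of a person's group-mates fall in the same arm, so DE is about 1 + s(m − 1)ρ/2. In the last row this is 1 + 0.50 × 5 × 0.30/2 = 1.375, which is 17% wider (√1.375 = 1.173).

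**Aim 2 factors.** The inflation also scales with the factor's own within-group correlation ρx: DE is about 1 + s(m − 1)ρρx.
- Factor fully shared within groups (ρx = 1): DE is as in the table. Simulated type I error of a simple two-proportion test at nominal 0.05 was 0.057, 0.063, 0.066, 0.082 and 0.144 at DE 1.05, 1.10, 1.15, 1.25 and 1.75.
- Factor partly shared (assume ρx = 0.3) with the last row's other inputs: 1 + 0.50 × 5 × 0.30 × 0.30 = 1.225, which is 11% wider (√1.225 = 1.107).
- Study arm: individual randomization makes ρx about 0, so DE is about 1.

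**Aim 1.** Same-arm pairs add to the variance of the arm difference and opposite-arm pairs subtract from it. Under 1:1 individual randomization the two cancel on average. Simulated type I error of the arm test was 0.047 to 0.053 in the five scenarios run.

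**The case against.** The strongest reply is that the effect may be negligible. Referral is one of six routes. According to the change history it entered with version 4.0 (approved January 2021), after enrollment of 400 had been approved in December 2019. A coupon pays out when the referred person attends a consenting session, even without consent, so redeemed coupons overstate enrolled recruits. Groups of six need all five coupon holders to enrol. Aim 2 already adjusts for HIV status, race and other characteristics that linked people share, so only the correlation left after adjustment matters. All of this stands. It argues for the lower part of the range, where widening is about 0 to 5%. It does not fill the gap, because the plan neither rules linkage out nor provides for measuring it.

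Two stronger readings are tempting.

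First, a reader might infer that coupons undo the safeguard of recruiting without "reference to home-based screening or HRA to lessen the population of persons with heightened concern and reservations about self-swabbing or HRA", since referrers know about kits and HRA. The documents do not support saying that the safeguard fails. Everyone is told about swabbing and HRA at consent, before randomization. Word of mouth is a separate listed route through which the same knowledge can pass. Reasons for declining and motives for enrolling are also collected.

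Second, a reader might infer that Aim 1 should be repeated without coupon recruits. That would not address correlation, and it would drop randomized participants although the Analysis section keeps all of them in primary and exploratory analyses.

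**Conclusion.** The concern holds as a conditional one. The recruitment design can produce linked participants and the link is recorded, but the planned Aim 2 models, the Aim 3 interval and any interval for overall compliance specify no allowance for it. If outcomes are positively correlated within referral groups, these intervals will be too narrow. Over the assumed inputs (s 10 to 50%, m 2 to 6, ρ 0.05 to 0.30) the design effect is about 1.0 to 1.75, the widening needed is about 0 to 32%, and coverage runs from about 95% down to 86%. None of these inputs comes from the documents. Referral over several generations could make groups larger than six.

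It would go too far to say that reported intervals are already wrong. The documents contain none, and they name no variance estimator. The Aim 1 arm comparison and the arm coefficient in Aim 2 are not at issue, provided that linked participants do not influence each other's compliance. Aim 2 factors that vary within groups, and outcome correlation that the adjustment covariates explain, are affected less. The simulated covariate test is a simple comparison, not the planned multivariable model.

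**What to change.** In the Analysis section, under Aims 2 and 3:

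1. Derive a referral-chain identifier from the recorded coupon numbers. A participant with no coupon link is a cluster of one.
2. Use cluster-robust or GEE standard errors for the Aim 2 models and for the single-proportion intervals for compliance and HRA uptake.
3. Report the share of participants enrolled by coupon and the within-chain correlation of compliance and HRA uptake.

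Leave the Aim 1 test as it is. The cost is a few lines of analysis text and one derived variable, with no new data and no change to study conduct. Intervals will be slightly wider if clustering is present and almost unchanged if it is not. One limit remains: partners or friends who arrive by word of mouth without a coupon will still be counted as unlinked.
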